9.5.2 Study size calculation

The sample size formula based on the normal approximation to the binomial is the following :

$$n = \frac{P \cdot (1 - P) \cdot (Z_{1-\alpha/2})^2}{e^2},$$

Where P is the expected proportion, e is one half the desired width of the confidence interval, and $Z_{1-\alpha/2}$ is the standard normal Z value corresponding to a cumulative probability of $1 - \alpha/2$ (e.g., if $\alpha = .05$ then $Z = 1.96$). As p is not known in advance, we consider it to be 50%. Such a hypothesis yields the most conservative i.e. largest sample size. If we consider a 2.7% precision and 95% confidence interval, we will need 1316 completed questionnaires.

For the conduct of survey, ideally the sample of 1316 physicians should be proportionally split between the selected countries based on the number of physicians in each country. However, due to large variance of the number of HCPs in targeted countries such a distribution would yield a too small number of interviews in smaller countries and would not allow the applicability of common statistical methods in those countries.

An empiric split of will be therefore implemented (

Table 2). Such sample will necessitate that the results of the study be weighted back according to the real proportion of physicians from IMS reference lists or available public information obtained through sources such as Eurostat (4) to order to allow the representativeness of the overall sample.

Usually, to ensure the robustness of statistical estimations at a given level of analysis (e.g. specialty or aggregated specialties per country), the sample size should not be lower than a threshold of 40 statistical units in each entity of this level. For analysis, less common specialties may need to be grouped. Subsequently, it will be necessary to weight back the study results according to the real proportion of physicians in order to determine the representativeness of the overall sample. In the event that the threshold of 40 statistical units (physicians per specialty in a country) would not be reached, then additional physicians of other groups will be recruited to compensate and preserve the sample size at country level.

Based on IMS Medical Radar experience from previous similar surveys and estimates, about 10-15% of physicians will not complete the questionnaire because they do not know TMZ (the questions on prescribing conditions would not be applicable to them) or because they have to interrupt the interview due to an emergency (rare). Taking this into account, recruitment of physicians should continue until 1320 analyzable questionnaires have been reached.

Table 2: Number of analyzable physician interviews required per country

Country	Sample size objective
Bulgaria	100
Czech Republic	80
Estonia	80
France	160
Hungary	100
Latvia	80

Lithuania	100
Poland	120
Portugal	150
Romania	100
Slovakia	100
Spain	150
Total Sample Size	1320

Sample adjustment:

Since the relative weight of each country and of each specialty in the sampling plan is different from its real relative weight in the target lists, the extrapolation of the raw survey results to the overall target population would not be relevant.

A sample adjustment will be performed. The survey results will be weighted to reflect the real proportion of the two countries and within each country to reflect the real proportion of each specialty in order to extend the survey results to the overall target population. Both unweighted (i.e. raw data) and weighted results will be presented in the report.

A weight variable will be applied to each statistical unit (i.e. the analyzable physician) during the results calculation in order to correct any over-or under-sampling that may have occurred for a country or specialty. This weight variable will indicate how many unit(s) of the population of interest an observation will count in a statistical procedure. Its value will change per country and per specialty. The weights will be normalized to obtain their sum equal to the sample size.

In order to fill-in each stratum of the sample survey from the external list and the IMS Medical Radar file, an independent sample will be selected per stratum through a simple random sampling without replacement.

In each specific stratum, physicians will be contacted according to the order of draw in this stratum. If a physician does not want to participate in the survey, the next one in order of draw will be contacted, and so on until the required number of physicians is met. If the target for a stratum is not achieved after the end of the initial list, an additional randomly sampled list will be prepared and the physicians contacted until the goal is reached or no names are left in that stratum. If the complete list of the IMS Medical Radar file has been exhausted in any particular stratum, a strategy will be determined to adjust the sample size within stratum with associated weighting.

It is to be noted that this sample is calculated to be representative as a whole (including all countries), not per country or specialty. Thus the subgroup analyses will not guarantee the same confidence intervals as the whole sample.

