4.8 Study size

The sample size calculation is based on the survey objective, *i.e.* to evaluate the prescribers and potential prescriber awareness of the updated safety information about TMZ in the DHPC and the updated SmPC.

For a confidence interval of 95% and a precision of 2.7%, a total of 1320 analyzable web-questionnaires will be needed for the overall sample in the twelve countries participating in the survey.

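### The ±2.7% precision stated for the overall sample makes no allowance for the unequal weighting that the plan itself requires

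*Protocol*

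**What the plan says.** Section 9.5.2 introduces its calculation thus: "The sample size formula based on the normal approximation to the binomial is the following". It defines precision as a half-width ("e is one half the desired width of the confidence interval"), sets the expected proportion ("As p is not known in advance, we consider it to be 50"%) and concludes: "If we consider a 2.7% precision and 95% confidence interval, we will need 1316 completed questionnaires". The synopsis in section 4.8 carries the figure to the overall sample: "For a confidence interval of 95% and a precision of 2.7%, a total of 1320 analyzable web-questionnaires will be needed".

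The same section 9.5.2 says that a split proportional to physician numbers would be ideal. It sets this aside because those numbers differ greatly between countries, and adopts the empirical split of Table 2, from 80 to 160 per country. Under the sample adjustment it concedes that "the relative weight of each country and of each specialty in the sampling plan is different from its real relative weight", for which reason raw results should not be extrapolated. Weights vary by country and specialty and are scaled to sum to the sample size.

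Section 9.7.1 adds that the unweighted overall line does not represent the countries' physician populations, and section 9.9.3 allows generalisation only after adjustment. The one caution about precision concerns subgroups: "the subgroup analyses will not guarantee the same confidence intervals as the whole sample".

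**The concern.** The formula P(1−P)z²/e² gives the precision of a simple random sample, or of a proportionally allocated one treated as such. The plan deliberately uses neither. When physicians in some strata stand for many more colleagues than physicians in others, the weighted estimate is less precise than its nominal sample size suggests.

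The stated ±2.7% therefore describes the unweighted total, which the plan says does not reflect the target population. The weighted overall proportion, the only one that may be generalised, has no stated precision. Because ±2.7% is the only quantitative justification of the study size, a reader of sections 4.8 and 9.5.2 will expect it for the population-level answer to the primary objective. The caution about subgroups strengthens that expectation, since it takes the whole sample as the benchmark.

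**Working it through.** **Inputs from the protocol.** P = 0.50, e = 0.027, 95% confidence (z = 1.96), total 1320 (9.5.2). Table 2 targets: Bulgaria 100, Czech Republic 80, Estonia 80, France 160, Hungary 100, Latvia 80, Lithuania 100, Poland 120, Portugal 150, Romania 100, Slovakia 100, Spain 150. Population shares by country and specialty are not given, so those below are assumptions.

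**Step 1: the plan's own figure.** n = 0.25 × 1.96² / 0.027² = 1317.4. The printed 1316 is within 2 of this, and 1320 covers it. At n = 1320 the half-width is 1.96 × √(0.25/1320) = 2.697%. The arithmetic is sound for a simple random sample.

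**Step 2: the weighted estimate.** With stratum population shares W_h, stratum sample sizes n_h and P = 0.5 in every stratum, the variance is 0.25·ΣW_h²/n_h. Relative to 0.25/n this is deff = n·ΣW_h²/n_h, and the half-width is 2.697% × √deff. By the Cauchy-Schwarz inequality deff is at least 1, with equality only if W_h = n_h/n in every stratum. The plan says that this equality does not hold, so deff > 1. No finite population correction is applied.

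**Step 3: country weighting alone, Table 2 sample sizes, assumed shares.**

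*(a) France, Spain and Poland together hold a share s, split equally; the other nine countries share the rest equally.* Since 1/160 + 1/150 + 1/120 = 0.02125, and the reciprocals of the other nine targets sum to 0.09417, deff = 1320 × [(s/3)² × 0.02125 + ((1−s)/9)² × 0.09417].

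| s | deff | half-width |
|---|---|---|
| 50% | 1.16 | ±2.91 |
| 60% | 1.37 | ±3.15 |
| 70% | 1.67 | ±3.48 |
| 80% | 2.06 | ±3.87 |

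*(b) Country sizes rise geometrically in the order of the Table 2 targets.*

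| largest : smallest | deff | half-width |
|---|---|---|
| 2:1 | 1.01 | ±2.71 |
| 5:1 | 1.07 | ±2.79 |
| 10:1 | 1.19 | ±2.94 |
| 20:1 | 1.35 | ±3.14 |
| 50:1 | 1.61 | ±3.43 |

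The 2:1 row shows that the loss would be trivial if country sizes followed Table 2. The protocol's reason for abandoning a proportional split is that physician numbers differ much more than a workable sample could. From 5:1 upward in (b), and over all of (a), deff runs from about 1.1 to 2.1 and the half-width from about ±2.8 to ±3.9 points.

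**Step 4: specialty, for illustration only.** If the four specialty groups were sampled equally, while the combined GP, internist and geriatrician group made up a share g of physicians and the other three groups split the rest equally, the extra factor would be 4·(g² + (1−g)²/3). This is 4 × (0.25 + 0.0833) = 1.33 at g = 0.5 and 4 × (0.64 + 0.0133) = 2.61 at g = 0.8. The protocol fixes no such split.

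**The case against.** The strongest reply is that 2.7% is a planning target at P = 50%, the least favourable proportion, and not a promise about the final interval. This stands in part. With deff = 1.5 the weighted half-width would still be 2.7% or less if the true proportion were about 79% or more (or 21% or less), and with deff = 2 if it were about 85% or more (or 15% or less). Strong differences between strata would also narrow the interval. A reader might therefore infer too much by concluding that the survey will certainly miss ±2.7%. The documents support only the narrower statement that, on the plan's own basis of P = 50% and with no credit for stratification, the stated figure does not apply to the weighted estimate.

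A reader might also multiply the country and specialty factors and arrive at half-widths of five points or more; for example, 1.67 × 2.61 is about 4.35, or ±5.6. The documents do not support that as an estimate. Table 2 fixes country totals only. Forty physicians in each of four groups would take 160 per country, a total that only France has. Section 9.5.2 also allows specialties to be grouped and shortfalls to be filled from other groups. Some specialty loss is likely, since the plan concedes that specialty shares differ from the real ones, but its size cannot be derived.

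Finally, a reader might infer that the reported intervals will be too narrow. They would be if weights scaled to the sample size were put into an ordinary Wald formula. However, the variance method for weighted results is commonly left to a statistical analysis plan, which is not at hand. The point here concerns the precision that the protocol states.

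**Conclusion.** The point holds in a limited form. Sections 4.8 and 9.5.2 give ±2.7% for the overall sample without any allowance for unequal weighting, although the allocation is deliberately disproportionate and only the weighted result is generalised. At P = 50% the correct statement for that result is 2.7% × √deff, with deff above 1.

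The direction follows from the protocol's own text; the size does not. Under the assumed country shares it is about ±2.8 to ±3.9 points, and more if specialty sampling is also far from proportional. These figures rest on P = 0.5 in every stratum and on physician shares that the protocol does not give.

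The consequence is moderate. The survey is descriptive, makes no statistical comparison and states no success threshold, so nothing in the protocol turns on the difference. It should be corrected because the remedy is cheap, but it does not show that the sample is too small.

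**What to change.** Before fieldwork, take the physician counts per country and specialty from the IMS reference lists, set them against the planned stratum targets, and compute deff = n·ΣW_h²/n_h. In sections 4.8 and 9.5.2, restate the overall weighted precision as 2.7% × √deff at P = 50%, and say that ±2.7% applies only to the unweighted sample or to a proportionally allocated one.

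Keep n = 1320 and the Table 2 allocation. The cost is a short calculation and a few changed sentences. The only downside is that the stated precision becomes less favourable; no further physicians are needed.

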9.6 DATA MANAGEMENT

The survey will be conducted according to the Standard Operating Procedures (SOPs) of IMS Medical Radar and IMS Real World Evidence Solutions.

Collected data will be entered and stored in a database specific to the survey and the country. A study database will be created by merging of databases of each country.

Data will be checked in terms of consistency before data analysis:

- removal of duplicates (if required),
- data labelling and data formatting,
- range and consistency checks for each variable to identify potential non admissible values,

- cross-check the consistency of data for related variables (if feasible).

The numbers of items with missing values will be indicated. Missing values are excluded from the calculation of the percentages. The study database will be locked after validation has been completed.

9.6.1 Data collection

The data collection period will last about 4 weeks in November 2014, and will be conducted in parallel in the twelve countries.

The survey will be conducted by IMS Medical Radar, a division of IMS Health specialized in the conduct of phone and web surveys for more than 20 years. IMS Medical Radar will create a web-based instance survey. The lists of physicians will be loaded into separate databases for the management of the survey.

As described previously (§9.5.1: Sampling plan and §9.5.2: Study size calculation), physicians will be randomly contacted, mainly by email and also by phone when needed, according to their stratum by the IMS Medical Radar team. Their recruitment will be done as follows:

- Physicians will be invited to participate in the survey (via phone calls or mails/emails). The survey background and objectives, the contact information for questions, and the proposed compensation will be explained to the physicians at this step. If they agree to participate in the survey, they will receive a link to access the survey and the instructions for the web-questionnaire completion.
- If the questionnaire is not completed and sent to IMS Medical Radar, the physicians will be sent a reminder by email one week after the start of the survey.
- If the target is not achieved in the stratum, a reminder by phone will be conducted 1.5 weeks after the start of the survey.
- If the questionnaire is still not completed and sent to IMS Medical Radar, the physicians will be sent a last reminder by email two weeks after the start of the survey.

If necessary, the recruitment will be performed by phone to achieve the target in a specific stratum.

A physician will be considered as contacted if he/she has:

- completed the survey and sent it back to IMS Medical Radar,
- refused to participate,
- was tentatively reached out to at least 5 times.

Moreover, a physician will be considered as unreachable if he/she has been contacted at least five times without any answer.

For each physician of the sample file, the number of contacts, and the date and time when he/she completed the web questionnaire will be recorded. The recruitments in each stratum will be stopped when the target is reached. If both physician lists have been exhausted in any particular stratum, the recruitments in this stratum will be prematurely ended and a strategy will be determined to adjust the sample size with associated weighting.

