7. RATIONALE AND BACKGROUND

Three pharmaceutical forms of TMZ- containing medicinal products are available in EU: 20 mg tablet, 20 mg/ml oral solution and 35 mg modified release (MR) tablet.

TMZ-containing medicinal products were indicated in EU for various cardiology, ophthalmology and otolaryngology indications.

Otolaryngology and ophthalmology indications included:

- Ancillary symptomatic treatment of vertigo and tinnitus and
- Ancillary treatment of visual acuity decrease and visual field disturbances due to vascular reasons

The indication in otology was authorized in 12 European Union Member States. The recommended dosage of TMZ 20 mg was one tablet three times a day, i.e. a daily dose of 60 mg. The equivalent dosage of TMZ 35 mg is one tablet in the morning and one tablet in the evening at mealtimes, i.e. a daily dose of 70 mg.

TMZ was indicated in ophthalmology in 7 countries in the European Union. In all countries, the recommended dosage of TMZ 20 mg is one tablet three times daily, i.e. a daily dose of 60 mg and the equivalent dosage of TMZ 35 mg is one tablet morning and evening, i.e. a daily dose of 70 mg (1).

Medicines containing TMZ are being marketed in Bulgaria, Cyprus, Czech Republic, Denmark, Estonia, France, Germany, Greece, Hungary, Ireland, Italy, Latvia, Lithuania, Luxembourg, Malta, Poland, Portugal, Romania, Slovakia, Slovenia and Spain (2)

On 22 April 2011, France had requested the Committee for Medicinal Products for Human Use (CHMP) to give its opinion under Article 31 of Directive 2001/83/EC on whether the marketing authorisation for TMZ-containing medicinal products will be maintained, varied, suspended or withdrawn.

The review conducted by the CHMP concluded that the evidence of the efficacy and safety in the ophthalmology and otolaryngology indications, initially suggested by the studies on the basis of multiple assessments was considered weak due to the methodology applied to the investigation and was no longer recommended since September 2012 (3).

Potential prescribers were informed of this change in the indication of TMZ through “Direct Healthcare Professional Communications” (DHPCs) and other appropriate notifications. A drug utilization study to monitor the compliance of prescribers regarding the restricted use of TMZ in ophthalmology and otolaryngology indications has been requested by the CHMP.

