8.2 OBJECTIVE

Primary objective:

- to evaluate the proportion of targeted physicians who received, understood and agreed to implement the updated information about TMZ provided in the DHPC

Secondary objectives:

- to evaluate the proportions of prescriptions within the licensed indication after the update of the SmPC
- to evaluate characteristics of prescribing conditions in terms of patient characteristics (age, gender) and prescription information (form of administration, dosage, new or repeat prescription, planned duration of usage, treatment situation, reason for choosing TMZ, discontinuation plan for patients already on TMZ).

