9.9.2 Limits inherent to web-surveys

The questionnaire includes general questions followed by specific ones. As the physicians may understand the right answer in subsequent questions, it would not be possible to go back in the questionnaire and edit answers in former questions.

In such surveys, the generalisation and external validity of the results is restricted to physicians who have an active email address and willing (and able) to answer a questionnaire online. These physicians may not be fully representative of the whole targeted population (12).

Among non-response bias, targeted physicians may also have activated filters in their mail box in order to block spams and unsolicited emails. They may not even see the invitation to participate in the survey if a very strict degree of message filtering is set. Having multiple email addresses could also be a critical situation. If the one used is not the primary address, or if the physicians do not check their email box frequently, they will not receive the invitation during the recruitment period. This is one of the reasons why the physicians will also be contacted by phone.

Moreover, web-surveys may promote social desirability bias which refers to the tendency of physicians to give socially desirable/expected responses instead of choosing those reflecting their current knowledge or behavior, e.g. physicians can copy-paste information collected online instead of giving their own opinions (12).

Social desirability can affect the validity of survey research findings, but the use of pre-populated items in the questionnaire could/tends to reduce this bias (13).

The access to the web-questionnaire interface will be strictly limited to the invited participants, with the possibility to participate only once and a traceability system. Thus stakeholder bias (multiple answers of people who have a personal interest in survey results and/or who incite peers to fulfill the survey in order to influence the results) or unverified respondents (when it is not possible to verify who responds) are not applicable.

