10.2 PHYSICIANS INFORMATION

Physicians participating in the survey will be informed about targets of the investigation, the nature of the transmitted data, the intended use of data, recipients of these data, and their right of access and rectification to their personal data, as well as their right of objection to use their data or to IMS keeping their data.

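### The invitation may disclose the DHPC and the withdrawn indications before question 1, and no safeguard in the protocol covers that cue

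*Protocol*

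**What the plan says.** Section 9.6.1 describes recruitment by phone, mail or email. At the invitation, "The survey background and objectives, the contact information for questions, and the proposed compensation will be explained to the physicians at this step". Next, "If they agree to participate in the survey, they will receive a link to access the survey". Reminders follow: an email at one week, a phone call at 1.5 weeks if the stratum target is unmet, and finally "the physicians will be sent a last reminder by email two weeks after the start of the survey". Section 10.2 adds that "Physicians participating in the survey will be informed about targets of the investigation".

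The primary objective in section 8.2 is "to evaluate the proportion of targeted physicians who received, understood and agreed to implement the updated information about TMZ provided in the DHPC". Sections 4.2 and 7 give the background: the evidence in the ophthalmology and otolaryngology indications "was considered weak due to the methodology applied to the investigation and was no longer recommended since September 2012", and prescribers were told of this by DHPC.

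Section 9.9.2 recognises cueing inside the form: "As the physicians may understand the right answer in subsequent questions, it would not be possible to go back in the questionnaire". It also admits that "physicians can copy-paste information collected online instead of giving their own opinions". Section 9.2.2 screens out physicians who do not know TMZ, at the start of the web questionnaire and so after the invitation.

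**The concern.** The survey is meant to show what the 2012 letter and SmPC update left in physicians' minds. If the invitation says that a letter was sent and which indications were withdrawn, some respondents will answer from the invitation, or from what it prompted them to look up. The item on the withdrawn indications is the most exposed. Self-reported receipt of the letter could be prompted too.

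The analysis cannot repair this. Every participant gets the explanation, so there is no uncued group for comparison. Weighting corrects only for country and specialty. The respondent/non-respondent comparisons in 9.7.1 and 9.9.1 use characteristics such as region, age, gender, practice type, country and specialty, none of which shows whether a physician was cued. A larger sample does not shrink the bias.

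**Working it through.** **Order of events.** Invitation with explanation (9.6.1), agreement, link, screener on knowing TMZ (9.2.2), then the questions. The rule in 9.9.2 stops a later question from informing an earlier answer. A cue in the invitation precedes all answers, so that rule does not touch it.

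**How much the background reveals.** Sections 4.2 and 7 give the ENT and ophthalmology withdrawal and the existence of the DHPC. The DHPC reproduced at the end of the protocol also covers restriction to add-on use in stable angina, movement-disorder contraindications, and renal impairment and the elderly. Sections 4.2 and 7 state none of these. The cue therefore matches one message among several.

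**The plan's precision (9.5.2).** Inputs: P = 0.50, z = 1.96, e = 0.027.

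n = P(1 − P)z²/e² = 0.25 × 3.8416 / 0.000729 = 1317.4

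The plan states 1316 and recruits 1320, so the figure reproduces. At n = 1320 the half-width is 1.96 × √(0.25/1320) = 0.0270.

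**Illustrative bias on the indication item.** Let K be true knowledge and f the share of unaware physicians who answer correctly because of the invitation. The documents do not give f; every value here is an assumption.

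Observed = K + f(1 − K), so bias = f(1 − K).

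At K = 0.50:

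| f | Observed | Bias (points) | Coverage of true K by nominal 95% interval |
|---|---|---|---|
| 5% | 52.5% | 2.5 | about 56% |
| 10% | 55% | 5 | about 4.5% |
| 20% | 60% | 10 | about 0% |

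Coverage is Φ(1.96 − b/se) − Φ(−1.96 − b/se), where b is the bias and se = √(o(1 − o)/1320) at observed proportion o. For f = 10%: se = √(0.55 × 0.45/1320) = 0.01369, b/se = 0.05/0.01369 = 3.65, and Φ(−1.69) ≈ 0.045. This treats the sample as unweighted simple random.

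The f at which the bias equals 2.7 points is 0.027/0.50 = 5.4%. Against the half-width at each K, the break-even f is:

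- K = 30%: 0.0247/0.70 = 3.5%
- K = 70%: 0.0247/0.30 = 8.2%

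**The primary-objective proportion.** If receipt and agreement are unaffected, the composite moves by at most f × A, where A is the share who received the letter and agree but lack this knowledge. A cannot exceed 1 − K, so the shift is no larger than the item's. If self-reported receipt is also cued, that bound does not hold.

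**The case against.** - **The invitation is not shown.** A general statement of purpose would also satisfy 9.6.1. A reader might infer that the answer is in fact given away, but the documents do not establish this. What stands is that nothing in the protocol prevents it.
- **Delay is not a fixed feature.** Section 9.7.2 describes agreement by clicking a link in the recruitment email, so completion can be immediate, and the phone reminder is conditional. This weakens any argument that respondents have days or weeks to look things up. It does not change that the explanation comes first.
- **Only one message is exposed.** The calculation cannot be applied to DHPC knowledge as a whole. This stands, and the figures above are confined to the indication item.
- **The bias need not run one way.** If the invitation introduces TMZ, physicians who would have been screened out may pass. They probably know less and are less likely to have received the letter, which lowers the proportion. This stands.
- **Online look-up is already a stated limitation.** Anyone completing the form alone can search once TMZ is named. Only the invitation's added effect is new, and nothing in the documents sizes it.
- **Physicians must be informed.** Section 10.2 requires this, and section 10.1.1 commits to EphMRA guidelines and local requirements. The defect is therefore the missing limit on content, not the act of informing. Withholding the drug name would go further than is needed.

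**Conclusion.** The point holds in limited form. The protocol fixes an explanation before question 1, leaves its content open, and words its own aims and background so that they name the DHPC and the withdrawn indications. The matching knowledge item and self-reported receipt may be cued, and 9.9.2 does not cover it.

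The likely direction for the indication item is upward; the screener could act the other way. The size is unknown. The 5.4% break-even is an illustration at the plan's 50% value, for one stand-alone item; the composite would shift less if receipt is unaffected. The documents do not support reading this as proof that the primary result is inflated, or that the whole knowledge measurement is lost. It is a gap that is cheap to close before fieldwork and cannot be repaired afterwards.

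**What to change.** 1. Amend 9.6.1: invitations, call scripts and reminders give the general purpose (a survey on prescribing and medicines information), duration, compensation, data use and contact. They do not mention the DHPC, its content or the withdrawn indications.
2. Give the full background and objectives on a closing page, after the answers are locked.
3. Align 10.2: general purpose before participation, detailed objective after it, subject to EphMRA and local rules.
4. List residual cueing by the invitation among the limitations in 9.9.

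The cost is rewording the recruitment texts and adding one closing page. No sample-size figure changes. A less specific invitation may slightly lower participation, and the disclosure rules of the twelve countries must be checked first.
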